## **6.2           IMPORTANT PROTOCOL DEVIATIONS**

Each protocol deviation must be assessed to determine whether it is an IPD. For definition of IPDs, and for the process of identification of these, refer to the BI reference document "Identify and Manage Important Protocol Deviations (iPD)" ([2](#)).

This is an open label, long term safety trial, all analyses will be performed based on the treated population only, i.e., no Full analysis Set or Per Protocol Set will be defined for analyses of efficacy. Since no confirmatory efficacy testing is planned, no efficacy related IPDs leading to exclusion from analysis set are defined. Efficacy, safety and GCP related IPDs are included in Section 4.1 of the Integrated Quality and Risk Management Plan (IQRMP).

Patients with iPD B.01, i.e., informed consent not available/not done, will be excluded from all analyses.

Table 6.2: 1 Important protocol deviations

Category / Code	Description	Comments	Excluded from
A	Entrance criteria violated		
A1	Inclusion criteria not met		
A1.01	Male or female patients, aged $\geq 18$ years	IC01  Also check versus derived age for patient.	None
A1.02	Women of childbearing potential (WOCBP) must use highly effective methods of birth control per ICH M3 (R2) that result in a low failure rate of less than 1% per year when used consistently and correctly.	IC03	None
A1.03	Have completed treatment and the EOT visit in the previous trial and are willing and able to continue treatment in 1368.17.	IC04	None
A2	Exclusion criteria violated		
A2.01	Have experienced study treatment-limiting adverse events during induction treatment with study drug	EC01	None
A2.02	Have developed any of the exclusion criteria from the original induction study	EC02, medical review	None
B	Informed consent		
B.01	Informed consent not available/not done	Date of informed consent missing or no signature on patient's "Declaration of Informed Consent"	All analyses
B.02	Informed consent too late	Date of informed consent not obtained prior to any study related procedure.  Minimum requirement for initial informed consent $\leq$ date of Visit 1/date of any study procedure	None
C	Trial medication and randomisation		
C3	Administration instruction not followed		
C3.01	Administration of potential contaminated drug	Study drug not prepared according to the instruction of administration  Medical review	None

Table 6.2: 1 Important protocol deviations (cont.)

Category / Code	Description	Comments	Excluded from
F	Study specific analysis		
F1	Other trial specific violation		
F1.01	Incorrect response assessment leads to assignment to wrong trial part (i.e. re-induction or maintenance) or to continuation of intensified maintenance therapy (following disease flare treatment)	Medical review	None
F1.02	Disease flare treatment used without sufficient evidence for a disease flare	Medical review	None
G	Other safety related violations		
G1	Pregnancy test not done for woman of child bearing potential, or pregnant during study	Pregnancy test not done at any visit where such is scheduled and the patient did not yet complete follow-up.	None

Source: BI reference document ' Identify and Manage Important Protocol Deviations (iPD)' [001-MCS-40-413] (2).

### 6.3 PATIENT SETS ANALYSED

#### *From CTP Section 7.3:*

*There will be 2 main patient populations in this trial for analyses: the Safety Analysis set for maintenance treatment (SAF-MT) and the Safety Analysis set for re-induction treatment (SAF-RT).*

#### Safety Analysis set for Maintenance Treatment (SAF-MT)

*This patient set includes all patients who received at least one dose of maintenance treatment in the extension trial. It will be the main analysis set for presentation of safety and efficacy during the maintenance part of the extension trial.*

#### Safety Analysis set for Re-induction Treatment (SAF-RT)

*This patient set includes all patients who received at least one dose of re-induction treatment in the extension trial. It will be the main analysis set for presentation of safety and efficacy during the re-induction part of the extension trial.*

In addition, the following patient sets are defined for analysis.

#### Enrolled set (ES)

This patient set includes all patients who sign the informed consent. This set will be used for disposition analyses.

#### Safety Analysis set (SAF)

This patient set includes all patients who received at least one dose of study drug in either the re-induction or maintenance periods. This set will be used for presentation of IPDs and patient listings.

**Safety Analysis set for Flare Treatment (SAF-FT)**

This patient set includes all patients who take at least one dose of disease flare treatment of 1200 mg SD i.v. in the extension trial. This set is the basis for efficacy and safety analysis on both the disease flare, and the post-flare treatment periods.

Note that the constitution of treatment sets will differ depending upon the number of patients entered into the trial at the time of each interim analysis.

**Table 6.3: 1** illustrates the data sets which are to be used for each category class of endpoints, as well as treatment periods to be reported for each data sets. For explanation of the different methods of handling missing data, cf. Section [6.6](#).

Table 6.3: 1 Patient sets and treatment periods analysed

Class of endpoints	ES	SAF	SAF-MT	SAF-RT	SAF-FT
Disposition	X		Overall maintenance TP	Re-induction TP	
Exposure			Pre-flare TP; Overall maintenance TP	Re-induction TP	Post-flare TP; Disease flare TP
IPDs	X				
Demographic/baseline characteristics		X		X	
Concomitant medication		X		X	
Secondary endpoint			Overall maintenance TP		
Further endpoint (including biomarker endpoint)			Endpoints defined for overall maintenance TP	Endpoints defined for re-induction TP	Endpoints defined for disease flare TP
Adverse event			Pre-flare TP; overall maintenance TP	Re-induction TP	Post-flare TP; disease flare TP
Safety lab, vital sign			Pre-flare TP; overall maintenance TP	Re-induction TP	Post-flare TP; disease flare TP

Note: MT=Maintenance Treatment; RT=Re-induction Treatment; FT=Flare Treatment; TP= Treatment Period

## **6.5 POOLING OF CENTRES**

All patients from all centres will be pooled for statistical analysis.

## **6.6 HANDLING OF MISSING DATA AND OUTLIERS**

Section 7.5 of the CTP describes the handling of missing data.

The original results (OR) approach implies the presentation of data exactly as observed (not using time windows and not setting values to missing).

OR analysis will be performed on parameters and endpoints that are either not affected by patients' rescue medication use (e.g. plasma concentration level of spesolimab, rescue medication use itself, or disease flare related endpoints), or, if it is not meaningful to apply any imputation rule for the replacement of missing values.

### 6.6.1      **Withdrawals**

The reasons for withdrawal from treatment will be reported as indicated on the eCRF.

### 6.6.2      **Efficacy endpoints**

**From CTP Section 7.5:** *With regards to the handling of missing data on those efficacy outcomes derived from the MCS, no missing data imputations are planned to be performed.*

In order to appropriately handle missing data in this trial, it is first necessary to define which are the inter-current events within each trial part, that lead to specific decisions being made upon the respective efficacy endpoint outcome, with such decisions being dependent upon the occurrence and timing of these events.

Any occurrence of the following will represent an inter-current event during both the re-induction and maintenance trial parts:

- Intake of rescue medication (as defined in [section 5.4.4](#)).  
Data after occurrence of such an event will be censored, and, handled subsequently according to the applicable missing data strategy described below.

In addition, any occurrence of the following will represent an inter-current event during the maintenance trial part:

- Occurrence of a confirmed disease flare (as defined in [Section 5.4.6](#)), or the intake of a dose of disease flare medication with 1200 mg BI 655130 SD.

Data after occurrence of such an event will be included in displays of the efficacy endpoints since treatment with spesolimab i.v. (to treat a disease flare) is not considered to represent a failed treatment outcome in this trial.

#### Efficacy imputation rules

The following rules apply for all treatment periods with defined efficacy endpoints. Missing data imputation, when performed, will not be done for missing assessments due to implementation of any cut-off date.

The following imputation strategy will be applied to the reporting of continuous efficacy data.

- Observed cases (OC) approach: prior to observing the applicable efficacy endpoint, data will be reported with no imputation performed on the missing data irrespective of whether the data is considered to be randomly missing, or missing due to prior occurrence of an applicable intercurrent event.

The following imputation strategy will be important for the display of binary efficacy data:

- No Response Imputation [NRI]: prior to observing the applicable binary efficacy endpoint, all missing data will be set to non-response irrespective of whether the data is considered to be randomly missing, or missing due to prior occurrence of an applicable intercurrent event. Only patients continuing at this visit per time window before interim cut-off will be included in the denominator.

The following imputation strategy will be important for the display of, i.e. safety laboratory data:

- Observed cases including values after any use of rescue medication (OC-IR): this approach is an extension of the OC approach which includes all values which were measured both before and after any rescue medication intake. The analysis using the OC-IR approach is then only based on the patients with observed data.

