3.3.4.1 Withdrawal from trial treatment

An individual patient is to be withdrawn from trial treatment if:

- A patient assigned to re-induction treatment does not achieve clinical response at week 12 compared to baseline of the original induction trial.
- A patient treated for a disease flare does not achieve clinical response (compared to baseline of the original induction trial) or clinical remission within 12 weeks after the initiation of disease flare treatment.
- A patient experience more than 1 confirmed flares during the trial.
- The patient wants to withdraw from trial treatment, without the need to justify the decision.
- The patient needs to take concomitant drugs that interfere with the investigational product. Please refer to [section 4.2.1](#) and [4.2.2](#).
- The patient can no longer be treated with trial medication for other medical reasons (such as surgery, adverse events, other diseases, or pregnancy).
- The patient has repeatedly shown to be non-compliant with important trial procedures and, in the opinion of both, the investigator and sponsor representative, is not willing or able to comply with the trial requirements in the future.
- A patient can be discontinued from trial medication at any time if in the opinion of the Investigator, continuation with trial medication is not in the patient’s best interest.
- For individual stopping rules related to specific adverse events, please see [section 4.2.1](#) “Other treatments and emergency procedures”.
- If peripheral neuropathy is suspected, treatment with spesolimab should be temporarily discontinued until a full neurological investigation has been conducted. After completion of the neurological investigation, treatment can be restarted based on medical judgement of the investigator.

Proprietary confidential information © 2022 Boehringer Ingelheim International GmbH or one or more of its affiliated companies

If a patient has not achieved clinical remission within the first 48 weeks of maintenance treatment, investigator should consider trial drug termination based on individual patient history and available alternative treatment options.

Given the patient's agreement, the patient will undergo the procedures for early treatment discontinuation and follow up as outlined in the [Flow Charts](#) and [section 6.2.3](#).

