4.2 OTHER TREATMENTS, EMERGENCY PROCEDURES, RESTRICTIONS

4.2.1 Other treatments and emergency procedures

If the patient requires additional medical therapy or dose increase of baseline ulcerative colitis medication (other than BI 655130 (SPESOLIMAB) to treat a disease flare or a reversion to the preceding higher daily steroid dose during tapering of steroids) to treat the underlying ulcerative colitis due to disease worsening (cf. [Table 2.1:1](#) Definition of Study Outcomes), the study drug must be discontinued and patients may receive conventional treatment for active disease. In case of disease flare during maintenance treatment period, patient must be provided with disease flare treatment (single i.v. dose of 1200 mg BI 655130 (SPESOLIMAB) infusion) followed by intensified maintenance treatment with 600mg BI 655130 (SPESOLIMAB) q6w.

In case of undue safety risk for the subject, the subject should discontinue study treatment at the discretion of the investigator. If the subject receives a live virus vaccination during the study, the subject must discontinue study treatment.

Systemic steroids dosed intravenously or orally for less than 24 hours as treatment of infusion or anaphylactic reactions are permitted and do not lead to treatment discontinuation (see [Table 4.2.2: 1](#)).

If mild-to-moderate infusion or anaphylactic reaction had already occurred in the very same patient in the past, pre-treatment with steroids before next IMP administration is permitted as secondary prophylaxis.

Locally administered steroids as e.g. intraarticular, nasal inhalation or intraocular administration are allowed, but their application has to be carefully monitored and reported in CRF (see [Table 4.2.2: 1](#)).

Management of Adverse Events:

Infusion reactions / Systemic hypersensitivity including anaphylactic reaction

In case of infusion reactions / systemic hypersensitivity including anaphylactic reaction emerging during or after infusion / injection(s) of study drug, the investigator should consider in accordance with severity of the reaction and local standard of care to:

- Immediately interrupt the infusion / Stop further injections
- Treat with systemic anti-histamines, intravenous steroids, and in case of a severe allergic reaction (e.g., anaphylactic reaction) epinephrine

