**5.2.2       Secondary endpoint(s)**

Proportion of patients with clinical remission (CR) at week 336 of maintenance treatment (as defined in [Table 9.1.1: 1](#))

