## 7. PLANNED ANALYSIS

### *General Remarks*

The format of the listings and tables will follow the BI guideline "Reporting of clinical trials and project summaries" (001-MCG-159) ([7](#)).

The individual values of all patients will be listed, including those collected during the off-treatment period. Listings will generally be sorted by country, centre number, patient number and visit (if visit is applicable in the respective listing). (see [Section 7.8.1](#) below for details).

The following standard descriptive statistical parameters will be displayed in summary tables of continuous variables:

N	number of non-missing observations
Mean	arithmetic mean
SD	standard deviation
Min	minimum
Q1	lower quartile
Median	median
Q3	upper quartile
Max	maximum

Statistical parameters will be displayed to a defined number of decimal places as specified in the BI guideline "Reporting of clinical trials and project summaries" ([7](#)).

Tabulations of frequencies for categorical data will include all possible categories and will display the number of observations in a category as well as the percentage (%) relative to the respective patient set (unless otherwise specified, all patients in the patient set irrespective of whether they have non-missing values or not). Percentages will be rounded to one decimal place. The category missing will be displayed only if there are actually missing values.

Disposition of the patient population for each trial part (re-induction or overall maintenance) will be summarised by presentation of the frequency of patients enrolled, treated, enrolled but not treated, who completed all doses of trial medication as planned, who completed the PE visit (EOT), who completed the trial (EOS), and who were prematurely discontinued, by reason. Additional summaries by the parent trial will be produced, and, summaries of the maintenance period disposition according to whether or not a patient experienced re-induction treatment or not will also be done. The frequency of patients with iPDs will also be presented; the iPDs will be listed per patient.

To better illustrate the long-term efficacy of the overall maintenance treatment (defined in [Table 6.1: 4](#)), a summary table regarding patient status over time will be added. The cumulative frequency of patients for the following categories will be displayed based on 12-week interval:

- ongoing on study medication, i.e., without early treatment discontinuation by the time point

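### The SAP's non-response rule keeps only undefined 'continuing' patients in the denominator; read literally, it drops treatment failures from interim displays and possibly from week 336

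*SAP*

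**What the plan says.** SAP 6.6.2 (Efficacy imputation rules) covers all treatment periods with efficacy endpoints. For binary endpoints under no response imputation (NRI), "all missing data will be set to non-response irrespective of whether the data is considered to be randomly missing" or missing because of an earlier intercurrent event. The next sentence sets the denominator: "Only patients continuing at this visit per time window before interim cut-off will be included in the denominator". The same subsection opens with a separate cut-off provision: "Missing data imputation, when performed, will not be done for missing assessments due to implementation of any cut-off date".

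The available text does not define 'continuing'. The nearest wording is in SAP section 7, where the patient-status table treats an ongoing patient as one who has not discontinued treatment early.

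The only secondary endpoint (SAP 5.2.2) is: "Proportion of patients with clinical remission (CR) at week 336 of maintenance treatment". SAP Table 6.3:1 assigns it to SAF-MT over the overall maintenance period. SAP 6.3 says of SAF-MT: "It will be the main analysis set for presentation of safety and efficacy during the maintenance part of the extension trial". Under SAP section 7, General Remarks, percentages are relative to "all patients in the patient set irrespective of whether they have non-missing values or not", unless specified otherwise.

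The protocol ends treatment for several kinds of failure. Under 4.2.1, when a patient needs additional colitis therapy, "the study drug must be discontinued and patients may receive conventional treatment for active disease". Under 3.3.4.1, patients are withdrawn if flare treatment has not worked within 12 weeks or if they have more than one confirmed flare. For patients without remission in the first 48 weeks of maintenance, the "investigator should consider trial drug termination based on individual patient history and available alternative treatment options".

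Protocol 7.5 plans no imputation for outcomes derived from the Mayo score. SAP 6.6.2 repeats that statement and then specifies NRI. SAP section 4 lists only the renaming of the patient sets as a change.

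**The concern.** The two NRI sentences pull in opposite directions. The first makes a patient with no value a non-responder. The second, taken at its word, removes that patient from the calculation if study drug has stopped. Patients who took rescue medication show the conflict best. Rescue is the one intercurrent event whose later data SAP 6.6.2 censors and hands to the missing-data rule, yet protocol 4.2.1 requires study drug to stop when such therapy is needed. These patients would usually not be continuing, so the imputation meant for them would rarely apply.

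A proportion calculated this way describes patients selected for not having failed, while its label suggests NRI on a treated set. The trial is descriptive and has no control arm or test, so the proportion is itself the efficacy result. SAP section 3 and protocol 7.4 foresee several interim analyses to support regulatory submissions, investigator's brochure updates and publications.

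**Working it through.** **Step 1. Does the denominator decide the result?** SAP section 5 limits efficacy data to the period from first dose to 16 weeks after the last dose. A patient who stopped years before week 336 has no usable week-336 value. NRI can count that patient as a failure only if the patient is in the denominator.

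**Step 2. Who would leave under the literal wording?** Patients who stopped for additional colitis therapy, failed flare treatment, more than one flare, an adverse event, or investigator or patient choice. A patient with one flare who responds to flare treatment stays: SAP 6.6.2 keeps those data and does not treat flare infusion as failure.

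**Step 3. Size.** Let N be the SAF-MT patients due at the visit, c those continuing and x those in remission, with every remitter among the c.

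- Continuing-only proportion = x/c
- All-SAF-MT proportion, with patients who stopped as non-response = x/N
- Ratio = (x/c)/(x/N) = N/c = 1/retention

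The ratio depends on neither N nor x. For illustration, N = 80 (the synopsis figure for maintenance). Retention, and 50% remission among continuing patients, are assumed.

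| Retention | c | x | x/c | x/80 | Ratio |
|---|---|---|---|---|---|
| 50% | 40 | 20 | 50% | 25% | 2 |
| 30% | 24 | 12 | 50% | 15% | 3.3 |
| 20% | 16 | 8 | 50% | 10% | 5 |
| 10% | 8 | 4 | 50% | 5% | 10 |

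Now vary remission among continuing patients from about 30% to 70%, in whole patients:

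- 50% retention: 12/40 = 30% against 12/80 = 15%, up to 28/40 = 70% against 28/80 = 35%.
- 20% retention: 5/16 = 31.25% against 5/80 = 6.25%, up to 11/16 = 68.75% against 11/80 = 13.75%.

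**Step 4. Does any reported figure test the rule?** No. Protocol Table 1.4:5 is labelled NRI but restricted to patients who completed 12 weeks. Its percentages reproduce (for example 4/14 = 28.6% and 2/16 = 12.5%). Its re-induction denominators sum to 10 + 16 + 14 + 10 = 50, while the text gives 51. The table does not show whether the missing patient had withdrawn or was still on treatment at the cut-off.

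**The case against.** The strongest reply is that the sentence is only an interim rule. It ends with a qualifier about an interim cut-off, and the final analysis has none. The separate cut-off provision concerns imputation and does not say who is counted. Under the whole-set default, patients who had not reached a visit at an interim would stay in the denominator unless another sentence removed them. On this reading both NRI sentences have work to do: rescue users count as non-responders, and only patients not yet at the visit drop out.

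This reading is available, so a reader who infers that the rule certainly governs the final week-336 result goes further than the text allows. It does not clear the wording. At an interim, 'continuing' still excludes patients who stopped as well as those not yet due. At the final analysis, the whole-set default gives way to any other specification, and this sentence may be one. SAP 7.5.2 refers the secondary endpoint to section 7.6, which is not in the public copy; the final denominator may be stated there.

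Three other inferences are tempting but unsupported:

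- *Remission among those remaining would be high whatever the drug does.* The mandatory stopping rules concern lost response, repeated flares and added therapy, not absence of remission. At 48 weeks the investigator only considers stopping, so responders without remission may continue.
- *Attrition is known to be heavy.* The amendment rationale reports that over half of the first 24 induction responders relapsed or flared within 6 months. That was on the earlier maintenance regimen, and a first flare leads to treatment, not withdrawal. The figure is context only.
- *Every binary summary is distorted.* Non-responders to re-induction and to flare treatment are judged at week 12 itself, so those week-12 displays would normally include them.

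It is also fair that disposition by reason and a 12-weekly patient-status table will show attrition, and that the protocol acknowledges selection bias. Neither corrects a proportion whose denominator is unclear.

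**Conclusion.** The point stands in limited form. As written, the denominator sentence conflicts with the imputation sentence before it and, read literally, makes binary outcomes conditional on staying on treatment. This reaches at least the interim by-visit displays. Whether it reaches week-336 remission cannot be settled from the available text: two programmers could follow the same SAP and report proportions that differ by 1/retention. That is 2-fold at 50% retention and 5-fold at 20%, assuming that nobody who stopped counts as a remitter. The multiplier is exact under that assumption; the retention values are illustrative, because the documents give neither retention nor remission among continuing patients.

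Separately, NRI departs from the no-imputation statement in protocol 7.5, and SAP section 4 does not list it. The history table says that missing-data handling for binary endpoints was updated in version 3.0, without saying which sentence changed.

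**What to change.** Replace the denominator sentence in SAP 6.6.2 with:

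> The denominator is all patients in the analysis set for the period (SAF-MT for week 336). Patients who stopped study drug before the visit count as non-response. At an interim cut-off or early trial end, only patients still on treatment whose visit window had not closed by the cut-off are excluded.

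Show the proportion among continuing patients as a labelled supportive row. Reconcile NRI with protocol 7.5 and list it in SAP section 4 as a change from the protocol.

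The cost is one sentence, a denominator flag and an entry in section 4. The reported remission figure becomes less favourable. At an interim there is a further cost: patients who stopped before a visit was due count as failures, while patients of the same entry date who are still on treatment are left out, which pulls the interim proportion down. If that matters, an additional row limited to patients whose planned visit date fell before the cut-off, whether or not they had stopped, would show how much.
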